12.0 Follow-up and Record Retention

The initial study is anticipated to progress from initiation to completion in about 12 months. For each participant, the study will commence at enrollment and last until 16 weeks from randomization. Patient clinical outcomes will be collected. Identified data in the secure database will be stored consistent with record retention requirements, typically 5 years from completion of the research. De-identified dataset will be maintained for secondary analyses and to support the reproducibility of reports.

## **Introduction**

To improve care for patients with opioid use disorder (OUD), Vanderbilt has implemented an Addiction Consult Team (ACT) and a Bridge Clinic. The primary purpose of the Bridge Clinic is to facilitate discharge for inpatients who are being considered for medications for OUD (MOUD). Specifically, the Bridge Clinic provides patients with temporary access to treatment at an outpatient clinic while they are waiting to be accepted into a long-term clinic. This document describes the statistical analysis plan for a pragmatic, single center, randomized, controlled trial designed to evaluate the impact of the Bridge Clinic on improving care for patients with active OUD. This document has been prepared prior to final data collection and unblinding. Because inpatient providers may delay discharge for patients with OUD who lack a source of outpatient care for MOUD, it is hypothesized that OUD patients referred to the Bridge Clinic will have a decreased overall length of stay, will follow up with their Bridge Clinic provider, and will have a reduction in overall costs for care.

## **Population and design considerations**

### *Study Population:*

Inpatients at VUH with OUD being considered for MOUD who have not used the Bridge Clinic before and who do not have a fixed outpatient plan are considered potentially eligible for this trial. If the ACT considers MOUD is clinically appropriate for the patient, the patient does not have plans for outpatient care, and the patient has not been enrolled in this study previously, they are enrolled, randomized, and offered a referral to either Bridge Clinic or treatment as usual (TAU) depending on randomization.

### *Study Design:*

This study is designed as a pragmatic, single center, randomized, controlled trial comparing clinical outcomes between patients assigned to receive a referral to the Bridge Clinic and patients assigned to TAU.

### *Randomization:*

Randomization occurs at the individual patient level. The Bridge Clinic can only accept a limited number of patients, so eligible patients will be randomized in a ratio so that the Bridge Clinic is at capacity. To start, the ratio will be 1:1, and can be updated as often as bi-weekly to maintain the Bridge Clinic capacity. There has been no indication or need to change the ratio during the study.

### *Sample Size Considerations:*

We estimated about 700 patients per year would be eligible for this study, with a capacity for about 3-4 new patients a week to be seen at the Bridge Clinic. We expected about 2/3 of patients referred to the Bridge Clinic to make their first appointment. The mean length of stay was 15 days with a standard deviation of about 15 days. Assuming a reduced standard deviation of 10 days, with 700 patients a year and a 1:1 randomization ratio, we would have 80% power to detect a 3-day reduction in length of stay. If the standard deviation remains at 15 days, we would have 80% power to detect a 3.5-day reduction in length of stay. Due to COVID-19, enrollment was lower than expected and hospital inpatient experiences differed from historical data. Midway through the recruitment period, the overall, ungrouped distribution of length of stay was re-estimated based on participant experience. Based on the revised assumptions, to detect a 1.5-day

reduction in length of stay and assuming the observed common standard deviation is a good estimate, about 336 patients (168 per group) is needed to have 80% power.

## **Interventions**

Inpatients with OUD who are deemed eligible for this trial are enrolled and randomized. The patients are randomized to one of two treatment arms:

- a) Direct referral to a long-term outpatient addiction provider (TAU)
- b) Referral to Bridge Clinic for temporary care while a long-term outpatient addiction provider is identified (intervention)

## **Endpoints**

### *Primary Endpoint*

The primary endpoint is the overall index hospital length of stay. The index length of stay is defined as the time between the admission and time of discharge during the inpatient visit when the participant is identified as being eligible for the study.

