5.0 Enrollment/Randomization

Principal Investigator: [name]

Version Date: April 7, 2022

Study Protocol: Evaluating the Impact of the Bridge Clinic in Patients with Opioid Use Disorder

The Addiction Consult Team (ACT) will be notified of potentially eligible patients via an EPIC consult order or referral from the general or homeless psychiatry service. Those patients for whom an order for an addiction medicine consultation is placed will be evaluated by the ACT for MAT. If the ACT considers MAT to be clinically appropriate, the patient does not have set plans for outpatient care, and the patient has not been previously randomized in this study, they will be enrolled and randomized. All other patients will be treated with usual care without availability of referral to the Bridge Clinic.

Screening information from enrolled patients will be entered into REDCap. For patients meeting objective criteria but whom the ACT determine ineligible for MAT, the reason for not enrolling them will be collected.

Once eligibility is confirmed, the patient will be randomized to being offered referral to the Bridge Clinic or not, as described below. Randomization will occur at the individual patient level. Randomization ratio will start at 1:1 and will be updated as necessary, but no more frequently than bi-weekly, to maintain the Bridge Clinic at capacity.

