Data will be abstracted from the EMR, REDCap and the Research Derivative (RD). The Research Derivative is a database of clinical and related data derived from the Medical Center's clinical systems and restructured for research. Data is repurposed from VU's enterprise data warehouse, which includes data from StarPanel, VPIMS, and ORMIS (Operating Room Management Information System), EPIC, Medipac, and HEO among others. The medical record number and other person identifiers are preserved within the database. Data types include reimbursement codes, clinical notes and documentation, nursing records, medication data, laboratory data, encounter and visit data, among others. Output may include structured data points, such as ICD 9 codes or encounter dates, semi-structured data such as laboratory tests and results, or unstructured data such as physician progress reports. The database is maintained by the Office of Research Informatics under the direction of [name].

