### *Main Analysis*

The primary outcome variable (hospital index length of stay) will be compared between groups using an adjusted generalized linear model. Since the data are positive and may be skewed, like a gamma distribution, we may use a negative inverse link function, a proportional odds model, or transform the data.

In this analysis, group assignment is the main predictor variable. For drawing conclusions about the effect of the Bridge clinic, a critical p-value of 0.05 for the effect of treatment group assignment on the primary outcome will be used. The model will be adjusted for age, race, ethnicity, and area deprivation index. The influence of continuous variables will be assessed using restricted cubic splines with a minimum of three knots. We do not expect missingness in our primary outcome. If there are missing covariates, cases will not be excluded; we will use multiple imputation with predictive mean matching for missingness in adjusting covariates.

Secondary and implementation outcomes will be compared between study groups using adjusted generalized linear models, just as for the primary endpoint. Binary endpoints will use a logit link function. For counts, such as number of medication refills, either a zero-inflated Poisson or a negative binomial model will be fit.

Exploratory outcomes for OPAT patients will not be compared between study groups but will be reported by study group.

There may be missingness in secondary or implementation outcomes. If there are missing outcomes, these may be imputed if they occur in less than 5% of cases. Otherwise, the cohort for which the outcome is available will be described, along with the results of the model evaluating treatment effects in this cohort. All model results will be summarized with point estimates and 95% confidence intervals (CIs), which will be emphasized over p-values when reporting the results for secondary and implementation outcomes. No adjustments for multiplicity will be made.

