### *Differential treatment effects*

To determine whether effects of treatment on the primary endpoint depends on any of the baseline characteristics, we will test the interaction between the baseline characteristics and treatment effect in the regression model. If evidence of an interaction is observed using a threshold of  $p < 0.2$ , we will proceed to subgroup analyses. For categorical variables, endpoints will be compared between within categories. For continuous variables, we will display the partial effects plots showing how treatment effects change with the putative subgrouping variable.

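### Index length of stay includes time before randomization that the primary model leaves unadjusted; adding it as a covariate costs almost nothing and may gain power

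*SAP*

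**What the plan says.** The SAP, under Primary Endpoint, starts the clock at admission: "The index length of stay is defined as the time between the admission and time of discharge during the inpatient visit". Protocol 5.0 places randomization later in the same stay. A consult order or psychiatry referral comes first, then evaluation by the Addiction Consult Team (ACT), and then: "Once eligibility is confirmed, the patient will be randomized to being offered referral to the Bridge Clinic or not".

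The SAP's Main Analysis fixes the covariates: "The model will be adjusted for age, race, ethnicity, and area deprivation index". It adds: "The influence of continuous variables will be assessed using restricted cubic splines with a minimum of three knots". The form of the model is left open: "we may use a negative inverse link function, a proportional odds model, or transform the data". The conclusion rests on one test of group assignment at 0.05. Protocol 10.0 promises covariate adjustment without naming the covariates.

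Neither document lists time from admission to randomization as a covariate, as a baseline variable (Protocol 6.0; SAP, Descriptive Analysis) or in a sensitivity analysis. Neither reports its typical length or spread. Under Differential treatment effects, the SAP also says: "we will test the interaction between the baseline characteristics and treatment effect in the regression model", with subgroup analyses to follow at p < 0.2.

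**The concern.** Each patient's index stay is the sum of two parts: the time from admission to randomization, and the time from randomization to discharge. The offer of the Bridge Clinic can act only on the second part. The first is fixed before assignment and is an arithmetic component of the outcome, which makes it a natural adjustment covariate. None of the four planned covariates is a component of length of stay.

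If patients reach randomization at widely different points in their stay, the variation in the first part adds noise that the model could remove. What is at stake is precision or power for the single test on which the conclusion depends.

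**Working it through.** **Inputs.** From Protocol 10.0, Interim Analysis: log-scale mean ln 5.5, log-scale SD ln 2.7 = 0.993, a 1.5-day reduction, 168 per group, 80% power. From SAP, Main Analysis: alpha 0.05, taken as two-sided because the side is not stated. The 1.5 days are read as 5.5 to 4.0 days, so the effect is ln(5.5/4.0) = 0.318.

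**1. The plan's own figure.** n per group = 2 × (1.960 + 0.842)² × 0.993² / 0.318² ≈ 153, not 168. With 168 per group, SE = 0.993 × √(2/168) = 0.1084 and power = Φ(0.318/0.1084 − 1.960) = 83.6%. The documents do not explain the difference. For 168 to give exactly 80%, the log effect must be 0.304, or 1.44 days. Both starting points are carried below. The SD was estimated from total length of stay, so the noise from pre-randomization time is already in it.

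**2. Gain in a linear model of log length of stay.** If the new covariate explains a share R² of the variance, SE = 0.993 × √(1 − R²) × √(2/168). Every R² here is an assumption.

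| R² | SE | Interval width ratio, √(1 − R²) | Power, 5.5 to 4.0 days | Power, from stated 80% | Equivalent N, 336/(1 − R²) |
|---|---|---|---|---|---|
| 0 | 0.1084 | 1 | 83.6% | 80.0% | 336 |
| 0.02 | 0.1073 | 0.990 | 84.3% | 80.8% | 343 |
| 0.1 | 0.1028 | 0.949 | 87.2% | 84.0% | 373 |
| 0.2 | 0.0969 | 0.894 | 90.7% | 87.9% | 420 |
| 0.3 | 0.0907 | 0.837 | 94.0% | 91.8% | 480 |

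R² is relative to the unadjusted SD; any part already explained by the four planned covariates would reduce the gain.

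**3. What R² might be.** Simulation with assumed inputs: pre-randomization time lognormal, post-randomization time Weibull, the two independent, calibrated to the log mean and SD above. The offer shortens only post-randomization time, by a factor that takes the geometric mean to 4.0 days. The model is least squares on log length of stay, 168 per group, 4,000 trials, with and without a three-knot spline.

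| Median pre-randomization time, log SD | R² | Power, unadjusted to adjusted |
|---|---|---|
| 0.5 day, 0.5 | 0.006 | 85.0 to 85.2% |
| 1 day, 0.5 | 0.02 | 86.8 to 87.7% |
| 1 day, 1.0 | 0.10 | 85.7 to 90.6% |
| 2 days, 0.8 | 0.17 | 87.7 to 95.0% |
| 2 days, 1.0 | 0.27 | 86.7 to 96.6% |

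Adjusted type I error was 4.5 to 5.2%.

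**4. Dependence on independence.** With lognormal parts, a log-scale correlation of −0.3 between the two parts moves R² in the last three scenarios to about 0.03, 0.05 and 0.13. A correlation of +0.3 moves it to about 0.27, 0.36 and 0.45. The documents do not give even the sign.

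**5. Proportional odds.** Same last three scenarios, lognormal parts, stay grouped in tenths, 150 trials each. The adjusted-to-unadjusted SE ratio of the log odds ratio was 1.01 in all three. Power rose from 85 to 90%, 83 to 94% and 78 to 95%. In the last scenario the mean log odds ratio moved from −0.54 to −0.69. So the interval does not narrow; the conditional effect is larger.

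**6. Cost if the covariate explains nothing.** With q extra degrees of freedom the variance is multiplied by about 1 + q/(336 − q − 2). From the 80% start, power becomes 79.9% for q = 1 and 79.8% for q = 2.

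**7. Interaction screen.** In the linear simulation, the interaction of this covariate with group reached p < 0.2 in 17.1, 17.9, 19.7, 27.4 and 35.2% of trials across the five scenarios. It exceeds the nominal 20% only where pre-randomization time is long and variable.

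**The case against.** The strongest reply is that nothing in the plan is wrong. Overall index length of stay is the declared endpoint in Aim 1 and in the SAP. The analysis is a valid adjusted intent-to-treat comparison, and choosing one more prognostic covariate is optional. That stands, and it is why the point is an improvement and not an error.

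The gain may also be tiny: two of the five scenarios gain under one point. The largest gain assumes that the offer roughly halves all post-randomization time (a factor at the 0.48 end of the 0.48 to 0.68 range used), while Protocol 10.0 expects only about two thirds of referred patients to make a first appointment. This stands too. A smaller true effect would lower power with and without the covariate, but would not remove the gain in precision.

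A third reply is that one common effect is reported although the effect on log stay is expected to vary with pre-randomization time. Under 1:1 allocation, the linear model still estimates the average difference. Under proportional odds or another nonlinear option, the covariate changes what is estimated. The SAP already accepts this by adjusting for four covariates under those options, but it should say so.

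Stronger readings are tempting, and the documents do not support them:
- A reader might infer bias. Pre-randomization time is fixed before assignment and balanced on average by randomization.
- A reader might infer that the trial is underpowered because part of the stay cannot change. The SD and the 1.5-day target both refer to total stay, so the planned power already allows for this.
- A reader might infer that the clock should start at randomization. Aim 1 asks about the overall index stay.
- A reader might want to add an indicator for infection requiring IV antibiotics. Its value is uncertain: Protocol 2.0 makes the six-week stay conditional on no skilled nursing place, and Protocol 1.0 suspended eligibility of OPAT patients from December 2020.

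**Conclusion.** The point holds as a nearly free improvement in precision or power. The omission is plain from the text. Its consequence is neither bias nor a shortfall against the stated 80% power.

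For a linear model of log length of stay, the interval is 1, 5, 11 or 16% narrower at an assumed R² of 0.02, 0.1, 0.2 or 0.3, and power rises from 83.6% to about 84, 87, 91 or 94%. Under proportional odds the test can gain, but the interval does not narrow and the effect becomes conditional on the covariate. The negative inverse link was not examined, so the linear-model figures should not be carried over to it.

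The size of the gain is unknown. It depends on the spread of pre-randomization time and on its correlation with the remaining stay, and the documents give neither. The figures are illustrations and bound nothing in either direction. The case for acting is the asymmetry: about 0.2 points of power at risk against a possible gain of several points.

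**What to change.** Before unblinding, add time from admission to randomization to the adjustment set in the SAP's Main Analysis. Use a restricted cubic spline with three knots on the untransformed time scale if clock times are held. If only dates are held, use log(days + 1), so that same-day randomization is defined. Check which applies and write a single form into the SAP.

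State that:
- overall index length of stay and the intent-to-treat comparison are unchanged;
- this is an adjustment covariate only and is excluded from the interaction screen, because the relative effect on total stay is expected to vary with it by construction;
- under proportional odds or another nonlinear option, the estimated effect is conditional on this covariate.

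The cost is a few SAP sentences and one or two degrees of freedom in 336 patients. No new data collection should be needed. Protocol 6.0 says of the Research Derivative: "Output may include structured data points, such as ICD 9 codes or encounter dates". Protocol 12.0 times follow-up by randomization: "the study will commence at enrollment and last until 16 weeks from randomization", which implies that its date is recorded. If unblinding has already taken place, report the adjusted model as a labelled supplementary analysis.

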### *Secondary Endpoints*

Multiple secondary endpoints are prespecified for this trial. Secondary endpoints are collected for 16 weeks following randomization:

- a) Overall quality of life as measured by the Schwartz Outcome Scale-10 (SOS10). The SOS10 has ten questions scored on a 0 (never) to 6 (all or nearly all of the time) scale. A total score is computed as the sum across the 10 questions. If two questions are missing, a mean score can be imputed for the missing values to generate a total score. No further imputation will be used for this score. This is self-reported and captured at the 16-week follow-up call.
- b) Linkage to MOUD provider, defined as attending at least one visit with a MOUD provider after discharge, assessed by self-report at 16-week follow-up call.
- c) Self-reported buprenorphine-naloxone (or naltrexone) prescriptions filled (number filled) at the 16-week follow-up call.
- d) Any recurrent opioid use reported at the 16-week phone call follow-up.
- e) Number of recurrent opioid uses reported at the 16-week phone call follow-up.
- f) Number of ED visits or readmissions to VUH 16 weeks post discharge identified in the electronic medical record.
- g) Hospital and emergency department free days
  - a. Hospital free days will be calculated as a count of whole days during the 16 weeks the subject is not in the hospital. If the subject dies before the end of 16 weeks, hospital free days will be equal to -1.
  - b. Hospital and emergency department free days will be calculated as a count of whole days during the 16 weeks the subject is not in the emergency department or in the hospital. If the subject dies before the end of 16 weeks, emergency free days will be equal to -1.
- h) Any overdose reported at the 16-week phone call follow-up.
- i) Death in hospital or documented at the 16 week follow up or in the medical record.
- j) Costs of care, defined as total costs for all care episodes at VUMC 16 weeks post discharge.

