1.0 Study Summary

Title: Evaluating the Impact of the Bridge Clinic in Patients with Opioid Use Disorder

Study Aims:

- Aim 1: To determine whether referral to the Bridge Clinic reduces overall index hospital length of stay when compared to direct referral to a long-term outpatient addiction provider for patients with active opioid use disorder (OUD) being considered for medications-for-addiction treatment (MAT).
- Aim 2: To evaluate the effects of the same intervention in the same population on secondary outcomes including costs, care-linkage, readmission rates, self-reported buprenorphine or naltrexone fills, rate of known recurrent opioid use, and measures of overall quality of life.
- Aim 3: Evaluate fidelity outcomes including Bridge Clinic acceptance and attendance rates among those referred to Bridge Clinic and reasons why patients were not considered to be eligible for inclusion.
- Aim 4: Among the subgroup of patients with an infection for which a course of IV antibiotics is required, additionally evaluate whether access to the Bridge Clinic facilitates outpatient management of the antibiotic therapy, with consequent improvement in clinical (infection and mortality) and resource (inpatient days, time to discharge following a negative blood culture) outcomes.

Study Hypotheses:

- Primary: Among patients with active OUD being considered for MAT, index hospital length of stay will be shorter among patients randomized to referral to the Bridge Clinic than among patients randomized to no referral to the Bridge Clinic.
- Secondary: Among patients with active OUD being considered for MAT, total costs, readmission rates, and rate of recurrent opioid use will be lower while successful care-linkage, self-reported buprenorphine or naltrexone prescription fill rates and quality of life will be higher among patients randomized to referral to the Bridge Clinic than among patients randomized to no referral to the Bridge Clinic.
- Exploratory: Among patients with active OUD being considered for MAT who also have an infection requiring IV antibiotics, referral to the Bridge Clinic will result in lower resource use without worse clinical outcomes when compared with not being referred to the Bridge clinic.

Study Population: Inpatients with OUD being considered for medications-for-addiction treatment (MAT) who have not previously utilized Bridge Clinic.

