3.0 Rationale and Specific Aims

In order to rigorously evaluate the impact of the Bridge Clinic on improving care for patients with OUD, a randomized controlled trial is needed. Evidence generated in this way will support either the sustained implementation of the Bridge Clinic with scale up to meet demand, or sufficient evidence will accumulate to indicate the expected impact is not achieved and alternative approaches are needed to improve the system of care for OUD patients being considered for MAT. Given the overarching goal of evaluating the Bridge Clinic as it is operating, the specific aims of this study are to:

- **Aim 1:** To determine whether referral to the Bridge Clinic reduces overall index hospital length of stay when compared to direct referral to a long-term outpatient addiction provider for patients with active opioid use disorder (OUD) being considered for medications-for-addiction treatment (MAT).
- **Aim 2:** To evaluate the effects of the same intervention in the same population on secondary outcomes including costs, care-linkage, readmission rates, self-reported buprenorphine or naltrexone fills, rate of known recurrent opiate use, and measures of overall quality of life.

²McKay, J. R., Lynch, K. G., Shepard, D. S., & Pettinati, H. M. (2005). The effectiveness of telephone-based continuing care for alcohol and cocaine dependence: 24-month outcomes. *Archives of general psychiatry*, 62(2), 199-207. McKellar, J., Wagner, T., Harris, A., Oehlert, M., Buckley, S., & Moos, R. (2012). One-year outcomes of telephone case monitoring for patients with substance use disorder. *Addictive behaviors*, 37(10), 1069-1074.

Principal Investigator: [name]

Version Date: April 7, 2022

Study Protocol: Evaluating the Impact of the Bridge Clinic in Patients with Opioid Use Disorder

- Aim 3: Evaluate fidelity outcomes including Bridge Clinic acceptance and attendance rates among those referred to Bridge Clinic and reasons why patients were not considered to eligible for inclusion.
- Aim 4: Among the subgroup of patients with an infection for which a course of IV antibiotics is required, additionally evaluate whether access to the Bridge Clinic facilitates outpatient management of the antibiotic therapy, with consequent improvement in clinical (infection and mortality) and resource (inpatient days, time to discharge following a negative blood culture) outcomes.

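### SAP item f, on its natural reading, pools ED visits and readmissions in one count, and the SAP specifies no readmission-only analysis for the protocol's hypothesis of lower readmission rates

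*SAP*

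**What the plan says.** **Protocol.** The secondary hypothesis in section 1.0 is that "total costs, readmission rates, and rate of recurrent opioid use will be lower" in the Bridge Clinic arm. It does not name ED visits. Aim 2 in section 3.0 covers "secondary outcomes including costs, care-linkage, readmission rates, self-reported buprenorphine or naltrexone fills". Section 6.0 lists readmission and ED visits on separate lines among the endpoints followed for 16 weeks. Section 10.0 gives a general rule of logistic regression for binary outcomes, without naming readmission.

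**SAP.** Under Secondary Endpoints, item f is "Number of ED visits or readmissions to VUH 16 weeks post discharge identified in the electronic medical record". Under Main Analysis, "For counts, such as number of medication refills, either a zero-inflated Poisson or a negative binomial model will be fit"; no analysis of the components of item f is mentioned. Two other items touch on later hospital use:

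- Item g.a: "Hospital free days will be calculated as a count of whole days during the 16 weeks the subject is not in the hospital", with death before 16 weeks scored -1. The header to the list says "Secondary endpoints are collected for 16 weeks following randomization".
- Item j: total cost of all VUMC care in the 16 weeks after discharge.

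**The concern.** The intervention is meant to work through earlier discharge: in the SAP Introduction, "it is hypothesized that OUD patients referred to the Bridge Clinic will have a decreased overall length of stay". Readmission is the natural check on that, because a shorter index stay is a smaller gain if more patients return as inpatients. The protocol treats it so, with a directional hypothesis and an endpoint of its own.

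In item f, an ED visit without admission and a full readmission each add one. The pooled rate ratio answers a question about acute contacts, which is not the question in the hypothesis. A rise in readmissions can be offset by fewer ED visits, and a real fall can be hidden in the same way. The SAP also does not say whether an ED visit that ends in admission adds one or two. Protocol section 7.0 says the results will inform possible expansion of the clinic, so a readmission result matters to the decision.

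**Working it through.** The plan gives no readmission or ED rate, so there is no figure to reproduce. The main check compares definitions; the arithmetic only illustrates the consequence.

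**1. Does any SAP endpoint isolate readmission?**

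| SAP item | What it measures | Readmission isolated? |
|---|---|---|
| f | ED visits and readmissions, one count | No |
| g.a | Whole days out of hospital, death = -1 | No: days rather than events; on the header's window it includes the rest of the index stay |
| g.b | Days out of hospital and ED | No |
| j | Cost of all VUMC care after discharge | No: pooled over all types of care |

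**2. Can the components offset each other in item f?** Assumptions: 168 patients per arm (SAP, Sample Size Considerations); two-sided 0.05, borrowed from the primary analysis, with sidedness assumed; event rates assumed; ED visits meaning those not ending in admission. For arm means m0 and m1 and dispersion k,

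SE(log rate ratio) = √[(1/m0 + k)/168 + (1/m1 + k)/168].

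Power is for a Wald test. ED visits fall by the same absolute amount as readmissions rise.

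| Readmissions, control → Bridge | ED visits, control → Bridge | Pooled rate ratio | Readmission rate ratio | Power, readmission alone (k = 0 / 1 / 2) |
|---|---|---|---|---|
| 0.30 → 0.40 | 0.80 → 0.70 | 1.10/1.10 = 1.00 | 1.33 | 34% / 27% / 22% |
| 0.30 → 0.45 | 0.80 → 0.65 | 1.10/1.10 = 1.00 | 1.50 | 61% / 48% / 40% |
| 0.30 → 0.50 | 0.80 → 0.60 | 1.10/1.10 = 1.00 | 1.67 | 82% / 69% / 58% |

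In every row the pooled test rejects with probability 5%, its nominal level. Swapping the arms hides a fall in readmissions instead.

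**3. Interval width, second row with k = 1.**

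- Readmissions: SE = √[(1/0.30 + 1/0.45 + 2)/168] = √(7.556/168) = 0.212. The 95% interval around 1.50 is a factor of exp(1.96 × 0.212) = 1.52 either way, about 0.99 to 2.27.
- Pooled count: SE = √[(2/1.10 + 2)/168] = √(3.818/168) = 0.151. The factor is exp(1.96 × 0.151) = 1.34, so about 0.74 to 1.34 around 1.00.

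**4. Does the undefined counting rule matter?** Take the second row and suppose every readmission comes through the ED. Counted once, the pooled rate ratio is 1.00. Counted twice, control is 0.80 + 2 × 0.30 = 1.40 and Bridge is 0.65 + 2 × 0.45 = 1.55, a ratio of 1.55/1.40 = 1.11. The same patients give different answers. Here double counting weakens the offset rather than adding to it.

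**5. Does hospital free days close the gap?** The planned effect is 1.5 days (protocol section 10.0, Interim Analysis). Treat this as 1.5 mean days, all falling after randomization, and ignore deaths. The extra readmissions per patient that leave item g.a unchanged are 1.5 divided by the assumed days per readmission:

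- 9 days: 1.5/9 = 0.17, or 28 per 168 patients
- 6 days: 1.5/6 = 0.25, or 42 per 168
- 4 days: 1.5/4 = 0.375, or 63 per 168

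So item g.a can also stay flat while readmissions rise.

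**The case against.** Four points deserve weight.

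- **Item f might mean two counts under one letter.** That is possible, but less natural: it is one item with one count, whereas recurrent use is split into items d and e, and item g into two lettered parts. If two counts were intended, the same edit makes it clear.
- **The protocol still lists readmission separately.** This stands. A reader might infer that the readmission hypothesis has been dropped, or that the trial could never report on it. The documents do not support that: nothing in the SAP withdraws the protocol's separate endpoint, and protocol section 10.0 has a general rule for binary outcomes. What they support is narrower: the SAP, which governs the analysis, specifies no readmission-only analysis.
- **Other endpoints speak to the trade-off.** This stands in part. Net days out of hospital is a reasonable summary of whether earlier discharge pays off, and costs after discharge would include VUMC readmissions. Neither estimates a readmission rate.
- **The illustration is built to cancel.** True. A reader might infer that cancellation is expected, or that ED visits will dominate the count. The documents give no rates to support either.

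A composite of acute-care use is also a legitimate pragmatic endpoint. That justifies keeping the pooled count, but not leaving it as the only analysis that bears on a hypothesis about one component.

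**Conclusion.** The point holds as a mismatch between the protocol's hypothesis and endpoints and the SAP's analyses. This rests on the wording alone, with item f taken in its natural sense, and needs no assumed rate.

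The possible size does rest on assumptions. Over the rates shown, readmission rate ratios of 1.33 to 1.67 coexist with a pooled ratio of 1.00. Readmission alone would have 22% to 82% power at 168 per arm, so a separate analysis may not be decisive. It would still be useful, because the SAP puts intervals ahead of p-values for secondary outcomes. The primary comparison of index length of stay is not affected.

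**What to change.** Before unblinding, replace item f with two endpoints:

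- **f1:** number of readmissions to VUH.
- **f2:** number of ED visits to VUH that do not result in admission.

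Give each its own adjusted count model of the kind already planned under Main Analysis. State that one continuous ED-to-inpatient episode counts once, as a readmission; other conventions are defensible, but one must be fixed in advance. Keep the pooled count as a supportive summary, and draw the conclusion on the readmission hypothesis from f1.

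The cost is a wording change and two component models in addition to the pooled one. Encounter and visit data are already among the sources in protocol section 6.0. Each component will have a wider interval than the pooled count (in the illustration, a factor of 1.52 for readmissions against 1.34), and there will be more secondary results without multiplicity adjustment.
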